4 STUDY DESIGN

4.1 OVERVIEW OF STUDY DESIGN

This is a Phase 2, open-label study of umbralisib, a PI3K delta inhibitor, administered in combination with ublituximab, a glycoengineered anti-CD20 mAb, to subjects with treatment naïve Follicular Lymphoma (FL) or Small Lymphocytic Lymphoma (SLL).

Daily doses of oral umbralisib will be administered for a duration of 24 cycles (approximately 24 months), in the absence of disease progression, unacceptable toxicity, or withdrawal from treatment. Two safety run-in cohorts of 3 - 6 subjects each at a dose of 600 mg and 800 mg umbralisib will first be enrolled to evaluate for key immune mediated toxicities. In the absence of unacceptable toxicity, enrollment will proceed with all subjects receiving 800 mg umbralisib. A fixed dose of 900 mg of ublituximab will be administered on Days 1, 8, and 15 in Cycle 1 and Day 1 of Cycles 2-6, Cycle 9 and 12. Ublituximab will be administered through Cycle 12. Treatment cycles are 28 days.

PET scans must be done at screening, within 14 days prior to Cycle 6 Day 1, and to confirm CR (if applicable). During the study period, all subjects will be evaluated for response by CT (if contrast CT is contraindicated MRI with a non-contrast CT Chest should be completed) within 14 days of Day 1 of Cycles 3, 6, and 12. After Cycle 12, subjects should be evaluated for response by CT (if contrast CT is contraindicated MRI with a non-contrast CT should be completed), approximately every 6 cycles through cycle 24, unless clinically indicated sooner (at the discretion of the treating physician).

After 24 cycles (approximately 24 months) of treatment, subjects will discontinue study medication and be followed for progression-free survival. Subjects who discontinue study drugs will have an End of Treatment visit within 30 days from the last dose of study drug. After cycle 24, subjects should have response assessment at least every 12 months or more frequently as medically indicated.

Subjects who discontinue from study treatment (for reasons other than progressive disease or completion of therapy), will have an End of Treatment visit within 30 days from the last dose of study drug. Follow for PFS as below:

- Months 1-24 approximately every 6 months
- Months 25 and beyond at least every year

Safety will be evaluated continuously throughout the study.

Up to 50 subjects are expected to be enrolled in this study.

4.2 SAFETY RUN-IN

A 3 + 3 approach will be utilized to evaluate safety during the safety run-in phase. Three subjects will first be treated at 600 mg umbralisib in combination with ublituximab for 1 cycle (28 days). If 1/3 subjects experience an unacceptable toxicity (defined below), 3 additional subjects will be enrolled at the same dose level. If >1/6 subjects at 600 mg experience an unacceptable toxicity, it

will be deemed to exceed the MTD and enrollment to the study will stop. If $\leq 1/6$ subjects experience an unacceptable toxicity at 600 mg, then 3 subjects will be enrolled to receive 800 mg umbralisib in combination with ublituximab for 1 cycle (28 days). If $1/3$ subjects experience an unacceptable toxicity, 3 additional subjects will be enrolled at the same dose level. If $>1/6$ subjects at 800 mg experience an unacceptable toxicity, it will be deemed to exceed the MTD and enrollment to the remainder of the study will proceed at 600 mg umbralisib. If $\leq 1/6$ subjects experience an unacceptable toxicity at 800 mg, then enrollment will proceed for the remainder of the study at 800 mg umbralisib.

An unacceptable toxicity will be defined as the occurrence of transaminitis, colitis, pneumonitis, or rash during Cycle 1 that is:

- Grade ≥ 3 and persists for >7 days without resolution despite supportive care; or
- Any grade treatment emergent toxicity that results in treatment discontinuation.

4.3 REGISTRATION AND ENROLLMENT

Prior to participation, subjects must willingly consent to the study after being informed of the procedures to be followed, the experimental nature of the treatment, potential benefits, alternatives, side-effects, risks and discomforts. Only eligible subjects will be enrolled onto the study.

Investigators will use an interactive web response system (IWRS) to register and enroll subjects to study UTX-TGR-203. Upon entering subject information into the IWRS, investigators will receive a unique subject identifier. This confirmation must be received by the site prior to dispensing study drug to the participant. Further details about the subject registration process using the IWRS system will be outlined in the Study Manual.

4.4 STUDY SITES

Up to 15 trial centers in the United States may participate in this study. Enrollment is expected to be completed in approximately 12-16 months.

4.5 DISCONTINUATION FROM STUDY TREATMENT

Subjects will be discontinued from study treatment for any of the following reasons:

- Disease progression
- Intolerable toxicity related to study drug
- Subject requests to withdraw consent or discontinue treatment
- Pregnancy
- Inability of the subject to comply with study requirements
- Conditions requiring therapeutic intervention not permitted by the protocol
- Non-compliance/lost to follow-up
- Investigator discretion
- Discontinuation of the study by the Sponsor
- Completion of 24 months of therapy

Subjects who discontinue from study treatment (for reasons other than progressive disease or

completion of treatment) should continue to be followed for progression-free survival (PFS).

Follow for PFS as below:

- Months 1-24 approximately every 6 months
- Months 25 and beyond at least every year

After withdrawal from protocol treatment, subjects should be followed for AEs for 30 calendar days after their last dose of either study drug. All new AEs occurring during this period must be reported and followed until resolution, unless, in the opinion of the investigator, these values are not likely to improve because of the underlying disease. In this case the investigators must record his or her reasoning for this decision in the subject's medical records and as a comment on the electronic Case Report Form (eCRF).

All subjects who have CTCAE Grade 3 or 4 laboratory abnormalities at the time of withdrawal should be followed until the laboratory values have returned to Grade 1 or 2, unless in the opinion of the investigator, it is not likely that these values are to improve because of the underlying disease. In this case, the investigator must record his or her reasoning for making this decision in the subject's medical records and as a comment on the eCRF.

5 STUDY ASSESSMENTS AND TREATMENT SCHEDULE

The table below lists all of the required assessments that should be performed at each study visit.

Cycle = 28 days	Screen	Cycle 1				Cycles 2-6					> Cycle 6		End of study ¹	LTFU
						C2	C3	C4	C5	C6	C9, 12, 18 and 24			
Procedure\Days	-28-1	D1²	D8	D15								Day 1	Day 1	
Medical history	X													
ECOG Performance Status³	X	X				X	X	X	X	X		X		X
Physical examination³	X	X	X	X	X	X	X	X	X	X		X		X
Vital signs (pulse, BP, temp, weight, resp)	X	X	X	X	X	X	X	X	X	X		X		X
BM Biopsy/aspirate⁴	X													
12-lead EKG	X													
Tumor evaluation⁵	X ⁵					X ⁵			X ⁵		X ⁵			X ⁵
FLIPI Staging⁶	X													
Serology: HCV, HBV, CMV⁷	X													
CMV Surveillance⁸						X			X		X			
Hematology (CBC including 5-part differential and platelets)⁹	X	X	X	X	X	X	X	X	X	X		X		
Serum Chemistry¹⁰	X	X	X	X	X	X	X	X	X	X		X		X
Cholesterol, LDL, HDL & Triglycerides¹¹	X	X				X	X	X	X	X		X		X
PT/INR	X													
Serum Pregnancy Test¹²	X													
Urine Pregnancy Test	X					X		X		X		X		
Core needle biopsy (optional)¹³	X			X										
Lymphocyte subsets¹⁵		X				X	X	X	X	X		X		X
PK Sampling (all pre-dose)¹⁶		X			X	X	X	X	X	X				
Concomitant Medications	X	X	X	X	X	X	X	X	X	X		X		X
AE Evaluation	X	X	X	X	X	X	X	X	X	X		X		X
Ublituximab		X	X	X	X	X	X	X	X	X		X ¹⁷		
Umbralisib (TGR-1202)			Administered orally daily with food through Cycle 24 ¹⁸											

¹ All subjects should undergo the end-of-study assessments listed within 30 days after treatment ends.

² Cycle 1/Day 1 procedures are all pre-dose study drug.

³ The screening physical examination, ECOG PS, cholesterol, LDL, HDL & triglycerides must be done \leq 7 days prior to initiation of treatment. However, if these initial examinations are obtained within 72 hours of Cycle 1 Day 1 they do not have to be repeated. Include assessment of B-symptoms. C1 (Day 8 & 15) and Cycle 2 (Day 1) physical exams have a \pm 3 day window, and a \pm 7 days for all visits after Cycle 2.

⁴ Subjects should have a bone marrow biopsy and/or aspirate within 90 days prior to Day 1 of Cycle 1 according to standard of care guidelines. Bone marrow biopsy and/or aspirate should also be obtained to confirm a CR. Bone marrow biopsy and aspirates should include FISH, flow cytometry and cytogenetics.

⁵ Baseline scans should be completed within 30 days prior to Day 1 of Cycle 1. All tumor evaluations after baseline have a +/- 14 day window. Radiology assessment includes a contrast enhanced CT scan of chest, abdomen, and pelvis (and neck as clinically warranted). If iodinated contrast is contraindicated, a non-contrast chest CT coupled with a gadolinium-enhanced MRI of the abdomen/pelvis (and neck as clinically warranted) is an acceptable substitute. PET using fluorodeoxyglucose (FDG) should be done at screening for all subjects then within 14 days of Cycle 6 and to confirm potential CR. Tumor evaluation should occur within 14 days of Day 1 of Cycles 3, 6, and 12, and approximately every 6 cycles thereafter through cycle 24. During LTFU, assessments should occur approximately every 12 months.

⁶ Lymphoma staging should be captured (see Appendix E) at baseline.

⁷ Serum virology to include HBsAg, HBc antibody, HCV antibody and CMV IgG and IgM. If HBc antibody, HCV antibody or CMV IgM is positive, subjects must be evaluated for the presence of active HBV, HCV or CMV by DNA(PCR). Serum virology to include HBsAg, HBc antibody, HCV antibody and CMV.

- ⁸ CMV only should be checked by PCR approximately every 3 cycles, as part of the subject's scheduled visit. If subject is CMV positive, stop therapy and provide supportive care per investigator discretion. CMV surveillance should discontinue 30 days after last dose of umbralisib.
- ⁹ The screening hematology must be done \leq 7 days prior to initiation of treatment. However, if these initial examinations are obtained within 72 hours of Cycle 1 Day 1 they do not have to be repeated. C1 (Day 8 & 15) and Cycle 2 (day 1), laboratory assessments have a \pm 3 day window, and a \pm 7 days for all visits after Cycle 2. Hematological parameters include the following laboratory tests: complete blood count consisting of hmeatocrit, hemoglobin, total white blood count (WBC) with 5-part differential, and platelet count.
- ¹⁰ The screening chemistry must be done \leq 7 days prior to initiation of treatment. However, if these initial examinations are obtained within 72 hours of Cycle 1 Day 1 they do not have to be repeated. C1 (Day 8 & 15) and Cycle 2 (Day 1) laboratory assessments have a \pm 3 day window, and \pm 7 days for all visits after Cycle 2. Chemistry panel includes the following: urea or blood urea nitrogen, creatinine, sodium, potassium, calcium, carbon dioxide, magnesium, phosphorous, glucose, albumin, total protein, total bilirubin, alkaline phosphatase, AST, ALT, GGT, uric acid, and lactate dehydrogenase.
- ¹¹ To be done \leq 7 days prior to initial of treatment. However, if these initial examinations are obtained within 72 hours of Cycle 1 Day 1 they do not have to be repeated.
- ¹² For women of child-bearing potential, a serum pregnancy teset will be performed at baseline (within 72 hours of Day 1 of Cycle 1) with a urine pregnancy test D1 of each cycle.
- ¹³ Core needle biopsy optional. If collected, sample at pre-dose (within 28 days) and one post dose anytime between Days 15 & 28 of Cycle 1.
- ¹⁵ Peripheral blood for lymphocyte subsets will be drawn on Cycle 1 Day 1 (pre-dose), Day 1 of Cycles 2-6, 9, 12, 18 and 24 and at end of study.
- ¹⁶ PK samples (plasma) will be collected according to the schedule in Section 5.1.2 (Central Laboratory Assessments). Additional PK samples may be collected outside of this schedule upon the occurrence of toxicity in order to correlate to plasma concentrations.
- ¹⁷ Ublituximab infusion only in Cycle 9 & 12 – no additional ublituximab after Cycle 12.
- ¹⁸ Review study drug compliance and document missed doses in medical record. Subjects are required to start prophylaxis treatment for pneumocystis jiroveci pneumonia (PCP) as well as antiviral therapy prior to Cycle 1 Day 1.

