6.2.3 CRITERIA FOR ONGOING TREATMENT

Continue treatment as per protocol provided that subject has:

- No intolerable toxicities related to study drug.
 - Treatment may be delayed to recover from toxicity
- No clinical or radiographic evidence of disease progression.
- Not withdrawn from the study for other reasons.

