6.3 DOSING DELAYS AND MODIFICATIONS

Subjects should be assessed clinically for toxicity at each visit using the NCI CTCAE v4.0 (<http://evs.nci.nih.gov/ftp1/CTCAE>) grading scale. Dosing will occur only if a subject's clinical assessment and laboratory test values are acceptable.

At the discretion of the Investigator, a dose re-escalation may be permitted for subjects who were dose reduced upon resuming umbralisib. Subjects that require dose reduction for events that are life-threatening should not be re-escalated. On second dose reduction for the same event contact the Medical Monitor prior to dose re-escalating to discuss management of the subject.

Holidays from study drug are discouraged. However, for subjects requesting a drug holiday without an adverse event, a holiday may be permitted at the discretion of the Investigator. The subject must be on study drug for 3 months to be eligible for a holiday from study drug >4 weeks.

Any subject in whom similar toxicity recurs at the reduced dose should be discontinued from further umbralisib treatment. Exceptions to this discontinuation rule on the basis of ongoing clinical benefit and acceptable/minimal clinical risk may be allowed following a careful assessment and discussion of risk versus benefit with the subject by the Investigator and with approval from the Medical Monitor.

If a subject discontinues only one study drug, the subject may continue treatment with the other study drug per the protocol. Please see Sections 6.3.1 and 6.3.2 below for specific guidelines regarding dose delay and/or modifications. Contact the sponsor prior to discontinuing any study drug(s).

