8.6.1 DURATION OF RESPONSE

Duration of response is defined as the time from documentation of a response to treatment to the first documentation of tumor progression or death due to any cause whichever comes first. Duration of the response will be summarized using n (sample size), mean, standard deviation, median, minimum, and maximum for the responders.

Duration of stable disease:

Stable disease is measured from the start of the treatment until the criteria for progression are met.

[figure not shown]
Progression-Free Survival:

Progression free survival (PFS) is defined as the time from study entry to the first documentation of tumor progression or death due to any cause whichever comes first. This variable will be analyzed via Kaplan-Meier methodology. The median PFS will be estimated.

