9.9.2.1 PROGRESSION-FREE SURVIVAL

Progression-free survival (PFS) is defined as the interval from Cycle 1/Day 1 to the earlier of the first documentation of definitive disease progression or death from any cause. PFS will be presented using the Kaplan-Meier method. Median time to event and the 95% confidence interval of the median times will be presented, if estimable. Median time to event will be tested against the null hypothesis value using a one-sample (one-sided) log-rank test.

Hypothesis testing for pairwise comparison will be performed using a log rank test via SAS Lifetest procedures. The median duration of PFS and the proportion of subjects alive and progression-free at 6, 12, and 18 months will be estimated using the Kaplan-Meier method. For each estimate, a 95% confidence interval will be reported.

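### PFS has two different start dates, and on-treatment scans follow cycle numbers without saying whether they stay on the calendar when treatment is held

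*Combined protocol and SAP*

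**What the plan says.** **PFS origin.** Section 9.9.2.1 says of PFS that it "is defined as the interval from Cycle 1/Day 1 to the earlier of the first documentation of definitive disease progression or death from any cause", and Section 2.2 agrees. Section 8.6.1 differs: "Progression free survival (PFS) is defined as the time from study entry to the first documentation of tumor progression or death". Study entry is not defined. Screening may begin on Day -28 (Section 5 table), and subjects are registered before drug is dispensed (Section 4.3).

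**Scan timing on treatment.** Footnote 5 of Section 5 reads: "Tumor evaluation should occur within 14 days of Day 1 of Cycles 3, 6, and 12, and approximately every 6 cycles thereafter through cycle 24". It adds: "All tumor evaluations after baseline have a +/- 14 day window". Section 4.1 states: "Treatment cycles are 28 days". The synopsis, 4.1 and 8 also set on-treatment scans by cycle number.

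**Holds.** Section 6.2.3 states: "Treatment may be delayed to recover from toxicity". Section 6.3.2 allows delay of either or both drugs. On holidays, Section 6.3 says: "The subject must be on study drug for 3 months to be eligible for a holiday from study drug >4 weeks". No maximum length is given for a hold or holiday. No section says whether the cycle count advances during one.

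**Where calendar time is used.** Subjects who stop treatment early are scanned about every 6 months up to month 24, then at least yearly (4.1, 4.5). Long-term follow-up scans are about 12 months apart. PFS is estimated at 6, 12 and 18 months (9.9.2.1).

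**The concern.** The two PFS origins cannot both be used. An earlier origin adds event-free days before treatment to every subject's time.

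The scan schedule raises a separate problem. A subject on a long hold is still nominally on treatment, so the month-based follow-up for discontinued subjects does not apply. If the next cycle starts late and its scan goes with it, the timing of assessment depends on toxicity and adherence, and progression is documented later. The trial has no comparator arm to share that error. Section 9.9.2.1 plans a one-sample, one-sided log-rank test, so absolute PFS times carry the inference. A later SAP can choose the origin and the censoring rules, but it cannot recover a scan that was not taken on time.

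**Working it through.** The documents available give no PFS figure to reproduce, so the check is calendar arithmetic plus an illustration.

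**Inputs.** From the protocol: 28-day cycles (4.1); scans at Cycles 3, 6, 12, 18 and 24 with a window of 14 days either way (Section 5, footnote 5); landmarks at 6, 12 and 18 months (9.9.2.1). Assumed: exponential PFS with a median of 18, 24 or 36 months; progression dated at the next scheduled scan; any hold falling between the Cycle 6 and Cycle 12 scans; cycle numbers moving with the hold. One month is 365.25/12 = 30.44 days.

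**Step 1: planned dates.** Days elapsed at Day 1 of Cycle k = (k - 1) × 28.

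| Cycle | Days elapsed | Week | Month |
|---|---|---|---|
| 3 | 56 | 8 | 1.8 |
| 6 | 140 | 20 | 4.6 |
| 12 | 308 | 44 | 10.1 |
| 18 | 476 | 68 | 15.6 |
| 24 | 644 | 92 | 21.2 |

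**Step 2: delay needed to cross a landmark.**
- Cycle 12 scan past month 12: 365.25 - 308 = 57 days, or 365.25 - 322 = 43 days if the scan uses the full late window.
- Cycle 18 scan past month 18: 547.9 - 476 = 72 days.

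**Step 3: effect on 12-month PFS.** Scan-dated 12-month PFS equals S at the last scan before day 365.25, where S(t) = 2^(-t/median).
- No hold: last scan at day 308.
- 28-day hold: day 336.
- 56-day hold: day 364.
- 84-day hold: the Cycle 12 scan falls on day 392, so the last scan before month 12 is at day 140.

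| Median (months) | True S(12) | No hold | 28 days | 56 days | 84 days |
|---|---|---|---|---|---|
| 18 | 63.0% | 67.7% | 65.4% | 63.1% | 83.8% |
| 24 | 70.7% | 74.7% | 72.7% | 70.8% | 87.6% |
| 36 | 79.4% | 82.3% | 80.9% | 79.4% | 91.5% |

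The three hold columns describe subjects who all have that hold. For the whole study, the change is the proportion held × (84-day value - no-hold value). At a 24-month median with 20% held, it is 0.20 × (87.6 - 74.7) = 2.6 points. Across the three medians the change is 1.8 to 3.2 points with 20% held, and 3.7 to 6.4 with 40%. A simulation of 400,000 subjects per scenario gave 1.7 to 3.3 and 3.6 to 6.5. The differences are simulation error, and the slightly wider range is the one quoted in the conclusion. A 56-day hold in 20% lowers the figure by 0.6 to 0.9 points in closed form.

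**Step 4: effect of the origin.** Suppose study entry is 28 days before first dose. Every PFS time, and so the median, gains 28/30.44 = 0.9 months. The on-schedule scans at days 140, 308 and 476 are then counted as days 168, 336 and 504. All still precede days 182.6, 365.25 and 547.9, and do so with 14 days added (182, 350, 518). The same scan precedes each landmark, so scan-dated 6-, 12- and 18-month PFS does not change for on-schedule subjects. The delay that carries the Cycle 12 scan past month 12 would fall from 57 to 365.25 - 336 = 29 days.

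**The case against.** The strongest reply is that moving cycle numbers are an inference. Umbralisib is taken daily, and either drug can be held while the other continues. Ublituximab is given only in Cycles 1 to 6, 9 and 12. Section 6.5 asks for visits as near as possible to their specified times. A site could keep calendar cycles through an umbralisib hold. This stands, so the effect on scan dates is conditional. But delaying an infusion tied to Day 1 of a cycle would naturally delay the cycle, and the text settles neither reading.

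Some protection exists. Holidays are discouraged, discontinued subjects move to month-based follow-up, and earlier scans are allowed on clinical grounds. As written in 4.1 and 8, that last provision attaches to scans after Cycle 12, so it does not clearly cover the gap between Cycles 6 and 12.

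Four stronger readings are tempting, and the documents do not support them:
- **A 28-day earlier origin raises 6-, 12- and 18-month PFS by about 2.3, 1.9 and 1.6 points.** That follows from a smooth exponential curve with a 24-month median. With progression dated at scans, the change for on-schedule subjects is zero (Step 4). Also, 28 days is an upper figure: screening hematology and chemistry are due within 7 days of treatment, so registration after eligibility is confirmed would probably fall close to first dose.
- **12-month PFS would read 88% against a true 71%.** That describes a group in which everyone has an 84-day hold. About 4 of those 17 points come from scan spacing alone, which fixed dates would leave in place.
- **Any hold inflates 12-month PFS.** Holds of 28 to 56 days bring the figure closer to the truth, so for those holds fixed dates would not improve this one estimate.
- **DOR is lengthened.** A late scan can delay the first documented response as well as progression, so the direction is not established.

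Finally, these are secondary endpoints, and at 50 subjects with PFS near 75% the binomial standard error is √(0.75 × 0.25/50) = 6 points, larger than the effect with 20% held. That limits the severity without removing the ambiguity.

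**Conclusion.** The point holds as a contradiction and a gap, both worth correcting. The contradiction is certain: two sections start PFS at Cycle 1/Day 1 and one at an undefined study entry. If study entry means registration, its cost is a lengthening of every PFS time and the median by the gap to first dose, at most about 28 days and probably less.

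The gap is also certain: scans are tied to cycle numbers, holds are open-ended, and the protocol does not say what happens to either count during a hold. Its numerical effect is conditional on scans moving with the hold. Under the stated model, an 84-day hold would add about 1.7 to 3.3 points to whole-study 12-month PFS if 20% of subjects had one, and 3.6 to 6.5 points if 40% did. The documents give no hold frequency or length, so those remain assumptions, as do the medians. The case for fixed dates is that assessment timing should not depend on toxicity or adherence; it does not rest on every estimate moving closer to the truth.

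**What to change.** - In Section 5 (footnote 5), Section 4.1 and Section 8, state that on-treatment scans are due at weeks 8, 20, 44, 68 and 92 from Cycle 1/Day 1, within 14 days either way, regardless of dose delays. Align the synopsis. These are the dates that Cycles 3, 6, 12, 18 and 24 already imply.
- Replace the PFS definition in 8.6.1 with a reference to 9.9.2.1, so that Cycle 1/Day 1 is the only origin.

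The cost is a wording amendment. The number of scheduled scans is unchanged, and no dosing, hold or holiday rule is touched. The small downside is that a scan may not coincide with a dosing visit when treatment has been delayed.

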3.2 EXCLUSION CRITERIA

Subjects who meet any of the following exclusion criteria are not to be enrolled to this study:

1. Subjects currently receiving systemic cancer therapy or previously received systemic cancer therapy for their lymphoma (i.e., chemotherapy, immunotherapy, biologic therapy, hormonal therapy, surgery, transplant, and/or tumor embolization).
2. Evidence of chronic active Hepatitis B defined as Hepatitis B surface antigen positive or Hepatitis B DNA positive by PCR (HBV, NOT including subjects with prior hepatitis B vaccination who are Hepatitis B surface antibody positive only;) or chronic active Hepatitis C infection (HCV) defined as Hepatitis C RNA positive by PCR, cytomegalovirus (CMV) DNA positive by PCR, or known history of HIV. If HBc antibody, HCV antibody or CMV IgG and/or IgM antibody is positive, subjects must be evaluated for the presence of HBV, HCV, or CMV by PCR - See Appendix F.
3. Subject has received wide field radiotherapy (including therapeutic radioisotopes such as strontium 89) \leq 28 days or limited field radiation for palliation \leq 14 days prior to Cycle 1/Day 1 or has not recovered from side effects of such therapy.
4. Primary central nervous system lymphoma (PCNSL) or known intracranial involvement, or leptomeningeal metastases.
5. Ongoing immunosuppressive therapy including systemic corticosteroids. Subjects are allowed to use topical or inhaled corticosteroids.
 - a. Corticosteroid therapy started at least 7 days prior to Cycle 1/Day 1 (prednisone \leq 10 mg daily or equivalent) is allowed as clinically warranted.
6. Known history of drug-induced liver injury, alcoholic liver disease, non-alcoholic steatohepatitis, primary biliary cirrhosis, ongoing extrahepatic obstruction caused by stones, or cirrhosis of the liver.
7. Any severe and/or uncontrolled medical conditions or other conditions that could affect their participation in the study such as:
 - a. Symptomatic, or history of documented congestive heart failure (New York Heart Association functional classification III-IV)[see Appendix C- NYHA Classifications]
 - b. Significant cardiovascular disease such as uncontrolled or symptomatic arrhythmias, congestive heart failure, or myocardial infarction within 6 months of enrollment.
 - c. Concomitant use of medication known to cause QT prolongation or torsades de pointes should be used with caution and at investigator discretion.

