5.1.1 LOCAL LABORATORY ASSESSMENTS

1. Hematologic profile and serum chemistry to include:

Hematologic Profile		
Hematocrit	Neutrophils	Platelet count
Hemoglobin	Lymphocytes	Absolute lymphocyte count
Erythrocyte count	Monocytes	Leukocyte count
Basophils	Eosinophils	Absolute neutrophil count
Serum Chemistry		
Albumin	Glucose	SGOT [AST]
Alkaline phosphatase	GGT	SGPT [ALT]
Bicarbonate/CO ₂	LDH	Total bilirubin
BUN	Magnesium	Total protein
Creatinine	Phosphorus	Uric Acid
Chloride	Potassium	
Calcium	Sodium	

2. Serum and urine pregnancy test.
3. Coagulation lab tests to include PT and INR.
4. Cholesterol, LDL, HDL and Triglycerides will be done at timepoint specified in the Study Assessment table
5. Serum Virology to include HBsAG, HBc antibody, HCV antibody, and CMV IgG and IgM. If HBc antibody, HCV antibody or CMV are positive the subject must be evaluated for the presence of active HBV, HCV or active CMV IgM by DNA (PCR). CMV should be checked by PCR approximately every 3 cycles as part of the subject's scheduled visit. If subject is CMV positive, stop therapy and discuss intervention with medical monitor CMV surveillance will discontinue 30 days after last dose of umbralisib (EOT visit)..- See Appendix F.
6. Subjects with low-grade lymphoma should have a baseline bone marrow aspirate and/or biopsy prior to study entry, according to standard of care guidelines, and then to confirm CR. Bone marrow biopsy and aspirates should include FISH, flow cytometry and cytogenetics.

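### Schedule footnote 7 triggers the screening CMV PCR on IgM, exclusion 2 on IgG and/or IgM; the two conflict for IgG-positive, IgM-negative subjects

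*Combined protocol and SAP*

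**What the plan says.** Four places in the protocol deal with CMV testing before enrolment.

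- **Synopsis and Section 3.2, exclusion 2** (same rule in both). One ground for exclusion is "cytomegalovirus (CMV) DNA positive by PCR". The criterion then says when the PCR must be done: if "CMV IgG and/or IgM antibody is positive, subjects must be evaluated for the presence of HBV, HCV, or CMV by PCR".
- **Section 5, schedule footnote 7.** The screening panel is "Serum virology to include HBsAg, HBc antibody, HCV antibody and CMV IgG and IgM". The condition for PCR that follows is "If HBc antibody, HCV antibody or CMV IgM is positive", in which case evaluation by DNA PCR is mandatory. IgG does not appear in that trigger. The footnote then repeats its panel sentence in a shorter form, with the two antibody classes dropped.
- **Section 5.1.1, item 5.** The panel again contains both antibodies. The instruction reads "If HBc antibody, HCV antibody or CMV are positive the subject must be evaluated for the presence of active HBV, HCV or active CMV IgM", followed by a reference to DNA PCR. The antibody class that counts as positive is not stated, and the thing to be looked for is written as an antibody although the test is for DNA.

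Separately, footnote 8 and Section 5.1.1 provide for CMV PCR during treatment, about every 3 cycles, with therapy to be stopped on a positive result.

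**The concern.** The exclusion is defined by a PCR result, so it can be applied only in a subject who has had the PCR. The antibody result decides who gets it. If two parts of the protocol set that trigger differently, two sites following the document in good faith can handle the same serology differently, and one of them will not know whether the subject meets exclusion 2.

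The footnote is part of the working instructions. Section 5 presents the schedule as the full set of assessments for each visit, and Section 5.1 says that laboratory tests are collected as that schedule specifies. Up to 15 sites may take part (Section 4.4).

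What is at stake is a safety gate at entry. A subject with CMV DNA who passes it untested would start both study drugs and would be found only by surveillance, where the protocol says to stop therapy. The primary response analysis is not shown to be affected.

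**Working it through.** No sample size, error rate or event count is involved, so the check compares the texts.

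**Step 1. Is the conflicting result observable?** Yes. The exclusion, footnote 7 and Section 5.1.1 all treat CMV antibodies as screening data, and the last two list IgG and IgM separately.

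**Step 2. Apply each rule to the four possible results.** The entry is whether a screening CMV PCR is called for.

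| CMV IgG | CMV IgM | Exclusion 2 | Footnote 7 | Section 5.1.1 item 5 |
|---|---|---|---|---|
| negative | negative | no | no | no |
| negative | positive | yes | yes | yes |
| positive | positive | yes | yes | yes |
| positive | negative | **yes** | **not triggered** | unclear |

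Exclusion 2 and footnote 7 agree in three rows and differ in one. In that row, Section 5.1.1 gives yes if a positive result on either antibody counts, and no if IgM is meant.

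**Step 3. Does anything else settle it?** No.
- Appendix F, to which exclusion 2 and Section 5.1.1 both refer, covers hepatitis B serology only.
- No statement says which section governs when two differ.
- As extracted, the CMV surveillance row of the schedule has no screening entry. The antibody trigger is therefore the only route to a CMV PCR before the first dose.

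**Step 4. What follows in the conflicting row?** At a site using footnote 7, CMV DNA status is unknown at enrolment.
- If the subject is DNA-negative, the subject was eligible anyway. What is lost is the verification, and Section 3.2 has been breached.
- If the subject is DNA-positive, an ineligible subject has been enrolled.

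**Step 5. How long could a missed case go undetected?** The column alignment of the surveillance row cannot be read reliably, so the first check is taken, as an assumption, to fall before dosing on Day 1 of Cycle 3 or Cycle 4. Cycles last 28 days. Ublituximab is given on Days 1, 8 and 15 of Cycle 1 and on Day 1 of the following cycles.
- Cycle 3 Day 1: 2 × 28 = 56 days of umbralisib, and 3 + 1 = 4 infusions.
- Cycle 4 Day 1: 3 × 28 = 84 days of umbralisib, and 3 + 2 = 5 infusions.

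**The case against.** The best defence is that the two texts can both be obeyed. Section 3 requires that no exclusion criterion be met, Section 4.3 allows only eligible subjects to be enrolled, and exclusion 2 makes the PCR mandatory after a positive IgG. Footnote 7 does not say that IgM is the only trigger, and it does not waive the PCR for anyone. A site that follows Section 3.2 tests every subject it should. That is right as far as it goes: the protocol does not authorise enrolment without the PCR, and a reader who inferred that it does would be going too far. It does not remove the problem, because the footnote gives a narrower trigger for the same test, and nothing tells a site to look past it. That some sites work from the footnote alone is a plausible risk, not something that the documents establish.

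A second defence is that surveillance limits how long a missed case stays hidden. It does, but only after dosing has begun, so it does not replace a test meant to decide entry.

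A third is that Section 5.1.1 is not a separate rule. This stands. Its wording can be read as covering either antibody, in line with exclusion 2. It is ambiguous, and the clear conflict is between exclusion 2 and footnote 7.

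**Conclusion.** The inconsistency is real and can be read directly from the text. It affects one of four antibody results, IgG-positive with IgM-negative. For those subjects, a site following footnote 7 would leave the CMV DNA exclusion unverified before dosing. How many subjects this concerns is unknown, because the documents give no seroprevalence.

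Three stronger readings are tempting, and the documents do not support them.

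- **That the same subject is eligible or excluded depending on the page used.** Antibody status does not exclude anyone; CMV DNA does. The outcome differs only for IgG-positive, IgM-negative subjects who are also DNA-positive, a smaller group that cannot be sized from the documents.
- **That a large share of the trial is affected.** With an assumed 30% to 70% of 50 subjects in the conflicting row, 0.30 × 50 = 15 and 0.70 × 50 = 35. The prevalence has no source in the documents, the result counts PCR tests and not subjects with CMV DNA, and 50 is the enrolment ceiling, whereas the trigger applies to everyone screened.
- **That a missed case means early discontinuation.** The surveillance text says to stop therapy but does not say that the stop is permanent, and CMV positivity is not among the reasons named in Section 4.5.

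The point rests on the wording alone. It deserves correction because it concerns a safety criterion at entry and is cheap to put right.

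**What to change.** Reconcile exclusion 2 in the synopsis and in Section 3.2, footnote 7 of the schedule, and Section 5.1.1 item 5 to a single CMV PCR trigger, stated in the same words in all four places. Which trigger applies is for the sponsor's clinical team to decide.

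In the same edit, remove the repeated panel sentence from footnote 7, state in Section 5.1.1 which antibody result counts and what the PCR is meant to detect, and make clear that Appendix F does not cover CMV.

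The cost is wording in an amendment. If the trigger in exclusion 2 is kept, no PCR is added beyond those that the criterion already requires. If another trigger is chosen, exclusion 2 itself has to be amended to match.
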